Pre-Op Appointment: After informed consent is obtained at the pre-op appointment, subjects undergoing mucogingival surgery will be given a sleep monitoring device (SleepImage® Ring 2019, SleepImage, Denver, CO) and will complete a baseline QoL survey (Qualtrics Survey, 2002, Qualtrics, Seattle WA).[11, 23-26] The sleep monitoring app will be downloaded on the subjects' phone and each subject will be trained on the function of the application by the principal investigators. Principle investigators (PI) will assist subjects to download the app and establish an account during the pre-op appointment. Subjects will create an account using their personal email, date of birth, and first/last name which will generate an unidentifiable subject number, which will be tracked in a secured file (Master Key of identifiable PII) accessible only by the PIs. The subject will accrue no fees upon creation of the account. Subjects will be instructed to contact the PIs with any malfunction or questions regarding the use of the application. The application will record sleep quality index (SQI), sleep efficiency, fragmentation, latency, duration, sleep opportunity and periodicity. This specific study will only utilize the SQI as the primary outcome variable. Subjects will be instructed to wear the device nightly throughout the study. The subject will be instructed to complete the same QoL questionnaire at 24 hours, 72 hours, as well as at the one week and two week post-operative appointments (study will last a total of three weeks).

Surgical appointment:

Blood (40 mL) will be collected at the beginning of the surgical appointment and spun using a horizontal centrifuge for the group receiving L-PRF (Horizon 6, horizontal PRF centrifuge machine, 2022, Drucker Diagnostics, Port Matilda, PA). L-PRF (test group selected via computerized randomization scheme with allocation 1:1 ratio) will be made from the blood collected as per manufacturer's protocol (4 vials of blood, centrifuged at 700g for 16 minutes at room temperature). Though some providers choose to use PRF routinely in mucogingival periodontal surgeries, for this study it will be for research purposes. Subjects not receiving L-PRF will have mucogingival surgery initiated without a prior blood draw.

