The periodontal surgery will be completed by preparing the recipient site as per standard of care. The tissue harvested from the roof of the mouth will be harvested by removing the upper layer of epithelium and connective tissue technique. This technique requires secondary healing to occur and is usually the area of most pain for subjects. [20, 21] The L-PRF will be placed on donor site (for research purposes) in the experimental group and secured with palatal stent for hemostasis (for research purposes) which will remain in place for 48 hours immediately after surgery. The control group will receive an available clotting material such as Helitape®, Helicote®, or Surgicel®, which is the standard of care, placed on the donor site and secured with a palatal stent for hemostasis with identical post-operative wearing instructions as the experimental group. All subjects will receive post-operative ibuprofen and acetaminophen for pain management. Time and amount of medication will be annotated and recorded at post-operative appointments.

Post-Op Appointments:

At the follow-up appointments, subjects will complete the one- and two-week questionnaires to evaluate their perceived QoL since the time of the surgical intervention (see questionnaire). The healing of the palatal harvest site will be evaluated by two calibrated clinicians using the Landry et al. healing index on a scale of 1-5 (see data collection sheet).[18] The provider will complete a routine post-operative examination which includes visualizing and palpation of surgical area for swelling, removal of sutures, evaluation of pain, noting any purulence upon palpation, noting any tenderness upon palpation of lymph nodes, and temperature obtained to indicate yes/no for infection. This data collection is considered standard of care. At the final follow-up appointment subjects will return the SleepImage ring to the primary investigators. If the sleep monitoring device is lost or damaged prior to the end of the trial, the study will cover the cost of replacement.

10.2 Data Collection:

Describe all the data variables, information to be collected, the source of the data, and how the data will be operationally measured.

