Statistical Analysis: All dichotomous or categorical variables will be presented initially as counts with percentages. Any analysis looking at two dichotomous or categorical variables will be compared using Chi-Square test. Continuous outcome variables will be initially assessed for normality by the Shapiro-Wilks test and then presented as means with standard deviations if normally distributed; independent t-test will be used determine any group differences between such variables (i.e. post-surgery – pre-surgery) or an ANOVA for three or more normally distributed variables. Otherwise, non-normally distributed outcomes will be presented as median and interquartile range (IQR) and analyzed using Wilcoxon Sign-Ranked Test or Mann-Whitney U Test for three or more variables. To test the relationship between QoL, sleep quality, healing outcomes, and intervention use, adjusted linear regression will be performed with guidance from a biostatistician. Significance will be set to $p < 0.05$. Any additional data collection or analyses will be determined in coordination and consultation with other investigators and the biostatistician through Qualtrics® and SleepImage® software. Subgroup analyses will be conducted in subjects with the following conditions: anxiety or depressive medications, smoking, sleep apnea, pulmonary disease, diabetes, autoimmune disorders, and chronic pain management as well as subject age and sex.

11.2 Sample Size:

Sample Size Estimation/Power Analysis:

The required sample size is 80, 40 subjects will receive the standard treatment and 40 the experimental intervention. It was calculated by using a priori analysis to provide a power of 80%, false positive rate of 5%, a 10% margin of error, and a 10% calculated dropout rate.

11.3 Total number of subjects requested (including records and specimens):

11.4 If you are recruiting by study arm, please identify the arms of the study and how many subjects will be enrolled in each arm

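### Sections 11.1 and 11.6 have no rule for ordinal outcomes, and neither univariate rule gives a sound between-arm test of the 1-5 healing index

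*Combined protocol and SAP*

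**What the plan says.** Section 9.3 lists healing status at one week and at two weeks as objectives under both aims. Sections 10.1 and 10.2 have two calibrated clinicians score the palatal site with a "healing index on a scale of 1-5 (see data collection sheet"). No section calls this score categorical, ordinal or continuous.

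Sections 11.1 and 11.6 carry the same analysis text. Three sentences could apply to the index:

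- **Categorical rule:** "Any analysis looking at two dichotomous or categorical variables will be compared using Chi-Square test".
- **Continuous rule:** a Shapiro-Wilk check, then an independent t-test, or ANOVA for three or more, if the data look normal. Otherwise outcomes are "analyzed using Wilcoxon Sign-Ranked Test or Mann-Whitney U Test for three or more variables".
- **Regression:** "To test the relationship between QoL, sleep quality, healing outcomes, and intervention use, adjusted linear regression will be performed".

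The arms are independent, formed by a "computerized randomization scheme with allocation 1:1 ratio" (section 10.1). Section 11.2 states: "The required sample size is 80, 40 subjects will receive the standard treatment and 40 the experimental intervention".

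**The concern.** A 1-5 healing score is ordered. Pearson's Chi-Square gives the same result if the labels 1 to 5 are shuffled, so it spreads its power over every kind of difference between the arms. It also gives no estimate of direction or size. The background in section 9.2 is directional: L-PRF is expected to improve healing. The sensible comparison is therefore one that looks for a consistent shift.

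The continuous route, read literally, does worse. The signed-rank test needs paired observations, and the two arms are not paired. At stake is whether a real shift in healing would be detected, and whether the choice of test is settled before the data are seen.

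**Working it through.** **1. The plan's own figure.** The 80 subjects cannot be reproduced for this outcome, because section 11.2 gives no endpoint, effect size or score distribution. What it does give is 40 per arm and 10% dropout, so 40 × 0.9 = 36 evaluable per arm. The significance level is 0.05, taken here as two-sided because sidedness is not stated.

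**2. The index read through each rule.**

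| Treated as | Test that follows | Problem |
|---|---|---|
| Categorical | Chi-Square | Order ignored |
| Continuous, non-normal | Signed-rank for two groups, by parallel with the t-test/ANOVA sentence; Mann-Whitney reserved for three or more | Paired test on independent arms; Mann-Whitney is itself a two-group test |
| Regression variable | Adjusted linear regression | Not stated whether healing is response or covariate |

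The normal branch of the continuous rule is not a realistic way out. In simulated five-level scores at 36 per arm, Shapiro-Wilk rejected about 100% of the time. A paired reading does not help either: the wound has no score before surgery, so the only natural pairing is week one with week two in the same patient, which is not the arm comparison.

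**3. Inputs for the power comparison (assumed).** Control scores 1 to 5 are 5/15/35/30/15%, with a proportional-odds shift. At odds ratio 3.0 the control cumulative odds 0.053, 0.25, 1.222 and 5.667 are each divided by 3. This gives cumulative probabilities 0.017, 0.077, 0.289 and 0.654, so L-PRF scores of 1.7/6.0/21.3/36.4/34.6%.

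**4. Simulated power, 36 per arm.**

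| Assumed odds ratio | Chi-Square | Mann-Whitney | Loss (points) |
|---|---|---|---|
| 2.5 | 32% | 56% | 24 |
| 3.0 | 48% | 71% | 23 |
| 3.5 | 59% | 82% | 23 |

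A repeat with 20,000 trials per row agreed to within two points.

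**5. Sensitivity to the assumptions (36 per arm, 20,000 trials each).**

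- Evenly spread scores, log odds ratio 1.2: 57.9% versus 79.9%, a loss of about 22.
- Central scores, log odds ratio 1.0: 39.6% versus 63.8%, about 24.
- Scores skewed high, log odds ratio 1.2: 54.5% versus 78.1%, about 24.
- Small shift (log odds ratio 0.5, odds ratio 1.65), five levels in use: about 9 to 10.
- Nearly all scores at 4 or 5: 7 at the small shift, peaking at about 15.
- Only levels 3 to 5 in use: 5 at the small shift, peaking at about 11.
- Large shift (log odds ratio 1.8): about 3 to 8, because both tests are then near their ceiling.
- A crossing, non-monotone difference: Chi-Square 74.8%, Mann-Whitney 27.7%, so the ranking reverses.

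**6. Analytic check.** A 1-df test with 80% power has noncentrality (1.96 + 0.84)² ≈ 7.85. The same noncentrality on 4, 3 and 2 df gives 59.5%, 64.5% and 70.9%, which are losses of 20.5, 15.5 and 9.1 points. The loss is set mainly by how many levels are actually observed.

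**7. Sparse cells.** The expected count per arm is 36 × the mean of the two arm proportions. At odds ratio 3.0, level 1 gives 36 × (0.050 + 0.017)/2 = 1.2 and level 2 gives 36 × (0.150 + 0.060)/2 = 3.8, both below 5.

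**The case against.** A reader might infer that the plan sends the healing index to Chi-Square and so gives up 20 to 25 points of power. The documents do not support that. They never classify the index, and the only analysis sentence that names healing outcomes is the linear regression. If healing is the response there, the order is used and direction and size are estimated. A t-test on the numeric score, a rough stand-in for that regression, came within about 5 points of Mann-Whitney. Mann-Whitney is also already named in the plan, although its use is misdescribed.

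Nor is the loss a fixed number. It peaks near the moderate shifts shown above and is smaller elsewhere. The sparse cells did not inflate the error rate: simulated Chi-Square size was 0.038 to 0.045. Healing is not the primary outcome, since section 10.1 gives that place to SQI. For the yes/no infection finding, Chi-Square is an ordinary choice.

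All of this stands, and it limits the point. It does not remove it. The regression sentence describes a relationship among four variables, without naming the response or the covariates, and does not present itself as the arm comparison at each visit. The two univariate rules remain order-blind in one case and, read literally, invalid in the other.

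**Conclusion.** The point holds as a gap with a faulty rule beside it. The plan does not state how the 1-5 index is compared between arms, and applying either univariate rule as written gives a weaker or an invalid test.

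The size is conditional on the Chi-Square rule being the one applied, on 36 per arm, and on a two-sided 5% level. The loss against a rank test is then at most about 20 to 24 points, with five populated levels and a moderate consistent shift. It is about 7 to 16 points for small shifts or when few levels are used, and 5 in the tested case that combines a small shift with only levels 3 to 5. The score distributions and odds ratios are assumptions; the documents give none. The signed-rank reading rests on the parallel with the preceding t-test/ANOVA sentence, and the wording is loose enough that the authors may have meant otherwise.

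**What to change.** In sections 11.1 and 11.6:

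1. State that the healing index at each visit is compared between the two arms with the Mann-Whitney (rank-sum) test, with a proportional-odds common odds ratio and 95% CI as the estimate.
2. Correct the rank-test sentence: Mann-Whitney for two independent groups, signed-rank for paired data.
3. Limit Chi-Square to unordered categories, with Fisher's exact test where expected counts are below 5.
4. Say how this test relates to the adjusted linear regression, including whether healing is the response there.
5. State how the two clinicians' scores become one score per patient per visit, since the test needs a single value.

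The cost is a few sentences, with no change to sample size or data collection. There is a small statistical price: a rank test has less power than Chi-Square for crossing differences, and the common odds ratio assumes proportional odds. Both are acceptable when the question is whether healing shifts in one direction.

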One of the potential ways that has shown promise is leukocyte-platelet-rich fibrin (L-PRF), an autologous fibrin clot that has been shown to positively influence postoperative healing cascades.[17] Rich in growth factors, L-PRF improves healing times through accelerated tissue migration at the site of surgery which ultimately reduces inflammation.[18] There have been reports of improved soft tissue healing, increased QoL, and patient reported reduction in pain following the use of L-PRF.[19-21] However, due to conflicting studies regarding the efficacy of L-PRF in comparison to control groups, further investigation is required.[22] Therefore, this prospective cohort study aims to evaluate the relationship between L-PRF, sleep, and perceived QoL on healing in patients undergoing periodontal mucogingival surgery compared to standard surgical intervention.

9.3

Objectives/Specific Aims/Research Questions:

Describe the purpose and objective(s) of the study, specific aims, and/or research questions /hypotheses

Specific Aim 1: Determine if subjects' self-perceived QoL after periodontal mucogingival surgery is influenced by differences in tissues healing with and without L-PRF at the tissue donor site.

Objective 1. Document subjects' perceived QoL pre/post-surgery with QoL questionnaire (pre-surgical, 24 hr, 72hr, one week post operative appointment, two week post-operative appointment).

Objective 2: Measure clinical indicators to determine presence of infection and healing status at one-week post-operative appointment.

Objective 3: Measure clinical indicators to determine presence of infection and healing status at the two-week post-operative appointment.

Specific Aim 2: Determine if tissue healing with and without L-PRF at the tissue donor site after periodontal mucogingival surgery influences quality and/or quantity of sleep before and during the healing phase.

Objective 1: Characterize pre-surgical sleep quality via SQI over a 3-7-day period using a sleep monitoring device for sleep and vital signs.

Objective 2: Characterize post-surgical sleep quality via SQI over a two-week period using a sleep monitoring device.

Objective 3: Measure clinical indicators to determine presence of infection and healing status at the one-week post-operative appointment.

Objective 4: Measure clinical indicators to determine presence of infection and healing status at the two-week post-operative appointment.

9.4 Study Design:

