17.1 Does the study involve the use of any unique non-medical devices/equipment?

☐ Yes ☒ No

18.0

FDA-Regulated Products

18.1 Will any drugs, dietary supplements, biologics, or devices be utilized in this study?

- ☐ Drugs
☐ Dietary Supplements
☐ Biologics
☒ Devices
☐ N/A

18.3 Device Details:

- ☒ Are device(s) in this research being used in accordance to the approved labeling?
☐ Are device(s) in this research being used in a manner other than its approved labeling?

When adding a device indicate in the details section of the device if the use is either used in accordance to the approved labeling or in a manner other than it's approved labeling

View Details	Device Name
	SleepImage Ring
Manufacturer/Supplier of Device	SleepImage
Where will the Devices Be Stored	AFPDS with the PI
Will Devices be supplied at no Cost	Yes
Is this a HUD (HDE)	No
HDE Number	
Who holds the IDE	PI holds the IDE

IDE details

Device measures sleeping patterns in subjects one week prior to surgery and two weeks post-operatively. This will be used in accordance to its FDA approved label.

18.4 Reporting Requirements for FDA-regulated research under IND and IDE:

Describe the process for complying with FDA regulatory requirements for adverse event reporting and adverse device effects reporting to the sponsor

SleepImage ring is strictly used as a monitoring device in this study and sleep efficiency results will be reported to the primary care provider in the case of adverse reporting.

18.5 Sponsor (organization/institution/company):

☒ N/A

If applicable, provide sponsor contact information:

[name]
[contact]
[contact] (office)
[contact] (mobile)

19.0**Research Registration Requirements****19.1 ClinicalTrials.gov Registration:**

- ☒ Registration is not required
☐ Registration pending
☐ Registration complete

19.2 Defense Technical Information Center Registration (Optional):

- ☒ Registration is not required
☐ Registration pending
☐ Registration complete

20.0**References and Glossary****20.1 References:**

- [1] P.M. Bartold, L.J. Walsh, A.S. Narayanan, Molecular and cell biology of the gingiva, Periodontology 2000 24(1) (2000) 28-55.
- [2] O. Al-Bayati, K. Font, N. Soldatos, E. Carlson, J. Parsons, C.A. Powell, Evaluation of the need to prescribe opioid medication to control post-surgical pain of different periodontal/oral surgeries, J Periodontol 92(7) (2021) 1030-1035.

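### The arm comparison is a t-test on post-minus-pre values with no baseline term in any named model; adjusting for the baseline already collected would be more precise for one degree of freedom

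*Combined protocol and SAP*

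**What the plan says.** Section 10.1 sets the primary outcome: "This specific study will only utilize the SQI as the primary outcome variable". The same section has a computerised 1:1 randomisation and a baseline QoL survey at the pre-op visit, repeated at 24 hours, 72 hours, one week and two weeks after surgery. Section 9.3, Specific Aim 2, Objective 1 provides the baseline for the primary outcome: "Characterize pre-surgical sleep quality via SQI over a 3-7-day period using a sleep monitoring device".

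Section 11.1 gives the comparison for normally distributed outcomes: "independent t-test will be used determine any group differences between such variables", with post-surgery minus pre-surgery as the example in brackets. Non-normal outcomes go to rank tests, also without a baseline term. The paragraph then adds a model: "To test the relationship between QoL, sleep quality, healing outcomes, and intervention use, adjusted linear regression will be performed with guidance from a biostatistician". Section 11.6 repeats this text almost word for word.

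Neither section says what the dependent variable of that regression is, what it adjusts for, whether the baseline value of the outcome is a covariate, or whether the regression or the t-test is the primary analysis.

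**The concern.** The t-test sentence can be read in two ways.

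- **Change score compared between arms.** Subtracting baseline fixes the slope of post on pre at 1. With equal SDs the true slope equals the correlation r, which is below 1, so subtraction over-corrects and leaves avoidable noise. If the arms differ at baseline by chance, the change score carries that difference into the estimate.
- **Post values compared with pre values.** This treats two measurements on the same subject as independent, and it does not compare L-PRF with control.

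The regression could repair the first reading, but as written nobody can tell whether it does. If it places post-surgical healing or sleep beside the intervention, its L-PRF coefficient is the effect not passing through those variables, not the total effect of assignment.

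What is at stake is precision in a trial of 80 subjects whose sample-size statement gives no effect size or SD, and therefore shows no spare power. A second cost is that the choice between t-test, rank test and an open regression stays open until the data are seen.

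**Working it through.** **The plan's own figure.** Section 11.2 gives 80 subjects (40 per arm) for 80% power, a 5% false positive rate, a 10% margin of error and 10% dropout. The figure cannot be rebuilt, because no effect size, SD or rate is given and the margin of error is not defined. Only the dropout step can be checked: 40 × 0.9 = 36 evaluable per arm.

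**Inputs.**
- 36 per arm, from section 11.2.
- 5% from section 11.1. Sidedness is not stated; two-sided is assumed.
- True difference of 0.5 SD of the post-surgical outcome: assumed, for illustration.
- Correlation r between baseline and post-surgical values: not in the documents; shown over 0.3 to 0.9.
- Equal pre- and post-surgical SDs: assumed here and relaxed below.

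**Variance factors,** in units of the outcome variance:
- change score: 2(1 − r)
- ANCOVA: 1 − r²
- ratio: (1 − r²) / [2(1 − r)] = (1 + r)/2

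The standardised difference is 0.5/√factor. Power is from the noncentral t, with 70 df for the change score and 69 for ANCOVA. At r = 0.5 the change score has factor 1.00 and standardised difference 0.50, giving 55% power. ANCOVA has factor 0.75 and 0.5/√0.75 = 0.577, giving 68%.

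With factor 1 and 36 per arm, 80% power needs a difference of 0.67 SD (0.6696 unrounded). The detectable difference is therefore 0.6696 × √factor. At r = 0.3, for example, it is 0.6696 × √1.4 = 0.79 for change and 0.6696 × √0.91 = 0.64 for ANCOVA.

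| r | Factor, change | Factor, ANCOVA | Ratio | Power at 0.5 SD, change v ANCOVA | Detectable difference (SD), change v ANCOVA |
|---|---|---|---|---|---|
| 0.3 | 1.40 | 0.91 | 0.65 | 42% v 59% | 0.79 v 0.64 |
| 0.5 | 1.00 | 0.75 | 0.75 | 55% v 68% | 0.67 v 0.58 |
| 0.7 | 0.60 | 0.51 | 0.85 | 77% v 83% | 0.52 v 0.48 |
| 0.9 | 0.20 | 0.19 | 0.95 | both above 99% | 0.30 v 0.29 |

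At r = 0.5 the ratio of 0.75 is worth 1/0.75 = 1.33, or one third more subjects. At r = 0.3 the change score (42%) does worse than ignoring baseline altogether, which has factor 1 and 55% power.

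**Unequal SDs.** With k the ratio of post to pre SD, the variance ratio is k²(1 − r²) / (1 + k² − 2rk).
- k = 1.5, r = 0.5: 1.6875/1.75 = 0.964, a saving of about 4%.
- k = 1.5, r = 0.7: 1.1475/1.15 = 0.998, almost nothing.
- k = 0.5, r = 0.5: 0.1875/0.75 = 0.25, a saving of 75%.

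The ratio never exceeds 1, because subtraction is the special case of adjustment with the slope held at 1.

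**Simulation** (36 per arm, 20,000 runs per setting, effect set so that the change-score test has 80% power). Type I error was near 5% for both methods (4.7% to 5.3%). ANCOVA power was 93.0%, 89.4%, 85.1% and 81.3% at r = 0.3, 0.5, 0.7 and 0.9. At r = 0.99 it was 78.9% against 79.4% for change, so the spent degree of freedom is visible only at the extreme.

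**The case against.** The strongest reply is that nothing here is an error. Under 1:1 randomisation a change-score t-test is unbiased, holds its type I error and already uses the baseline. That stands: a reader might infer that the planned test is invalid, and the documents do not support it. Regression to the mean matters only given a chance baseline imbalance, and does not bias the comparison over repeated randomisations.

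A second reply is that the plan does adjust, through its regression. This stands in part. Adjustment is under-specified rather than ruled out, and section 10.2 records age, sex, smoking and diabetes, which could serve as covariates. A reader might equally infer that the regression conditions on post-surgical healing or sleep and so distorts the L-PRF effect. The sentence allows that model but does not state it; regressing each outcome on intervention with adjustment is just as possible. Either way, the text does not say that baseline SQI or QoL enters.

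A third reply is that the gain may be small. SQI is recorded over several baseline nights and two weeks afterwards. Averaging tends to raise r, and the saving is only 5% at r = 0.9. This stands as a limit on the size, not on the direction.

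A reader might also see a conflict between the baseline windows in sections 9.3 ("Characterize pre-surgical sleep quality via SQI over a 3-7-day period") and 18.3 ("Device measures sleeping patterns in subjects one week prior to surgery and two weeks post-operatively"). A range of 3 to 7 days includes one week, so this is not a contradiction and forms no part of the point.

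**Conclusion.** The point holds as a recommendation on efficiency and specification. The named arm comparison has no baseline covariate, its wording admits a reading that does not compare the arms, and the regression beside it is too open to fill the gap.

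Under equal SDs, 36 per arm, two-sided 5% and a true 0.5 SD difference, the gain from ANCOVA is about 17, 12 and 6 power points at r = 0.3, 0.5 and 0.7. The exact size cannot be fixed, because the documents give neither r nor the SDs, and unequal SDs can shrink or enlarge it. The power figures apply only to the change-score reading of the t-test sentence.

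Two stronger statements should be avoided. The trial cannot be said to detect 0.67 SD as planned, since for change scores that figure needs r = 0.5. Nor is adjustment entirely free. Apart from the one degree of freedom, however, it is never less efficient than the change score.

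**What to change.** In sections 11.1 and 11.6, replace the t-test on change with a named primary arm comparison: a linear model of mean post-surgical SQI on assigned arm plus mean pre-surgical SQI. Analyse QoL in the same way, on arm plus baseline QoL. State which of the four post-surgical QoL time points is the main one, or how they are combined, and what replaces the rank-test fallback so that it too carries the baseline.

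Allow only pre-surgical covariates in the arm-effect model and list them. Pre-surgical is a safer term than pre-randomisation, because the documents do not say when randomisation falls relative to the baseline nights. Leave out healing index, length of surgery and harvest size.

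Report the regression linking QoL, sleep and healing separately, as an exploratory association, with its dependent variable and covariates named.

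The cost is SAP wording and one degree of freedom. No new data are needed, and the change should be made before outcome data are seen.

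### Five QoL scores per subject and nightly SQI are repeated measures, but the plan names no method for three or more of them, defines no per-subject SQI summary, and lists tests that do not match each other

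*Combined protocol and SAP*

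**What the plan says.** **Data collected.** Section 9.3 (Specific Aim 1) lists the QoL times as "pre-surgical, 24 hr, 72hr, one week post operative appointment, two week post-operative appointment", which makes five per subject. Section 10.1 gives the same post-operative schedule. For sleep, section 10.1 states "Subjects will be instructed to wear the device nightly throughout the study". Section 9.3 (Specific Aim 2) sets a baseline, "Characterize pre-surgical sleep quality via SQI over a 3-7-day period", and a follow-up, "Characterize post-surgical sleep quality via SQI over a two-week period using a sleep monitoring device". Section 10.1 adds "This specific study will only utilize the SQI as the primary outcome variable". There are two arms: "test group selected via computerized randomization scheme with allocation 1:1 ratio".

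**Tests named.** Section 11.1, repeated almost word for word in 11.6, gives:
- chi-square for categorical variables;
- for normally distributed outcomes, an independent t-test for group differences, with a parenthesis pointing to post-surgery minus pre-surgery, or "an ANOVA for three or more normally distributed variables";
- for non-normal outcomes, the Wilcoxon signed-rank test, or Mann-Whitney U when there are three or more variables;
- an adjusted linear regression relating QoL, sleep, healing and intervention, with a biostatistician's guidance.

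Neither section mentions a repeated-measures ANOVA, a mixed model, a subject effect, the QoL time point to be compared, or how a subject's nights of SQI are summarised.

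**The concern.** With two arms, an ANOVA for three or more variables is not needed for the treatment comparison. Its most natural use is across the QoL time points, where every subject contributes to every time. An ANOVA without a subject term treats those scores as coming from different people. It then leaves the stable differences between subjects in the error term and can hide real change over time.

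For SQI the gap is the unit of analysis. A subject has 3 to 7 pre-surgical nights and about 14 post-surgical nights, and the text does not say what single quantity enters the t-test. Some choices give a valid 5% test and others do not, and the plan gives no basis for telling which will be used.

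The list of tests also does not separate paired from independent data, so the analyst cannot recover the intended comparison from the names of the tests.

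**Working it through.** **Inputs from the documents.** 80 subjects, 40 per arm, 10% dropout (11.1, 11.2): 80 × 0.9 = 72 evaluable, 36 per arm. Five QoL times, four of them post-surgical (9.3). Two post-surgical weeks of nightly SQI: 2 × 7 = 14 nights (9.3, 10.1). Nominal alpha 0.05 (11.1). The figure of 80 cannot itself be reproduced, because no effect size or SD is given. Nothing below depends on how it was derived.

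**Assumptions.** The documents give no within-subject correlation ρ, so I use 0.3, 0.5 and 0.7. The simulations take equal correlation between all pairs of times, complete data, two-sided tests and total SD 1. They use 20,000 replicates for QoL and 4,000 for 14 nights.

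**Step 1: ANOVA across the five times.** With no time effect, the between-time mean square has expectation σ²(1 − ρ), while the error mean square without a subject term has expectation σ². The F ratio therefore centres near 1 − ρ = 0.7, 0.5 or 0.3 instead of 1, and the test rejects too rarely. A repeated-measures ANOVA removes the subject variance from the error. Error degrees of freedom are 5 × 72 − 5 = 355 without a subject term and 4 × 71 = 284 with one.

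**Step 2: pre versus post in the same subjects, analysed as two independent samples.** True SE divided by assumed SE is √(1 − ρ) = 0.837, 0.707 and 0.548. Type I error is about 2[1 − Φ(1.96/√(1 − ρ))]. At ρ = 0.5 this is 2[1 − Φ(1.96/0.707)] = 0.006.

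**Step 3: between-arm t-test on one value per subject** (a change score, or the mean of 14 nights). Subjects are independent, so the test should hold its level.

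**Step 4: worst case, nights or visits pooled as if independent.** Design effect DE = 1 + (m − 1)ρ; type I error is about 2[1 − Φ(1.96/√DE)].
- m = 14: DE = 1 + 13ρ = 4.9, 7.5, 10.1, giving 0.376, 0.474, 0.537.
- m = 4: DE = 1 + 3ρ = 1.9, 2.5, 3.1, giving 0.155, 0.215, 0.266.

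**Simulation results (type I error unless stated)**

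| Analysis | ρ = 0.3 | ρ = 0.5 | ρ = 0.7 |
|---|---|---|---|
| ANOVA over 5 times, no subject term | 0.008 | 0.001 | <0.001 |
| Repeated-measures ANOVA | 0.050 | 0.051 | 0.050 |
| Power, 0.3 SD shift at one visit, no subject term | 31% | 23% | 14% |
| Power, same shift, repeated measures | 55% | 72% | 93% |
| Independent t-test, pre vs post, same subjects | 0.019 | 0.006 | <0.001 |
| Between-arm t-test, one change score per subject | 0.051 | 0.049 | 0.048 |
| Between-arm t-test, 14-night mean per subject | 0.049 | 0.055 | 0.051 |
| Between-arm t-test, 4 QoL scores pooled | 0.15 | 0.22 | 0.27 |
| Between-arm t-test, 14 nights pooled | 0.38 | 0.49 | 0.55 |

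The 0.055 is within simulation error: √(0.05 × 0.95/4,000) = 0.0034, and 0.055 − 0.050 = 0.005 is less than two such errors.

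**Step 5: do the tests correspond?**
- If the parenthesis means one change score per subject compared between arms, the independent t-test is right. Its rank counterpart is Mann-Whitney, so the signed-rank test is wrong.
- If it means a comparison within subjects, the signed-rank test is right and the independent t-test is wrong.
- On either reading, Mann-Whitney is a two-sample test and cannot serve three or more variables.

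**Step 6: visit-by-visit testing.** Comparing the change from baseline between arms at each of the four post-surgical visits, unadjusted, gives about a 0.16 chance of at least one false positive. A primary contrast is therefore needed even when each individual test is valid.

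**The case against.** The strongest reply is that the plan is thin here rather than wrong. Several harsher conclusions are tempting, and the documents do not support them.

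- **That the planned p-values are wrong.** The text says only ANOVA, without a type. The absence of a subject term is inferred from the absence of any repeated-measures wording. The ANOVA could also be meant for factors that may have three or more levels, such as type of surgery, sedation or clinician experience (10.2), where it is legitimate. This stands. But if that is the intended use, the five-visit QoL series has no named test over time.
- **That the independent t-test is invalid.** The most natural reading of its parenthesis is a between-arm test of one change score per subject, which holds its level at 0.048 to 0.051. It fails only for paired values treated as two samples, or for pooled nights.
- **That nights or visits will be pooled, with false-positive rates of up to about 55%.** No section says so. Those rates are worst cases, not a description of the plan.
- **That nothing in the plan respects pairing.** The signed-rank test is a paired method, and a change score also uses the pairing. What is missing is a method for three or more repeated measurements.

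It is also fair to say that the power loss in Step 1 concerns change over time, whereas both Specific Aims turn on L-PRF versus no L-PRF. The loss does not carry over to a properly formed arm comparison.

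The biostatistician's guidance does not close the gap. It is attached to the regression and to unspecified additional analyses, and the regression's own unit of analysis is undefined.

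**Conclusion.** The point holds as a gap in specification with one conditional error and one definite inconsistency. The gap is that both main outcomes are repeated measures, and sections 11.1 and 11.6 give neither a method for three or more measurements per subject nor a per-subject SQI summary. The conditional error is that ANOVA across time points without a subject term is badly conservative and loses much of its power, by the amounts tabulated. This rests on 72 complete subjects, equal correlations and an assumed ρ of 0.3 to 0.7. The direction follows for any positive ρ of this form; the size depends on ρ. The definite inconsistency is the test pairing: one branch is wrong on either reading, and Mann-Whitney is misassigned.

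For the primary outcome, the same text permits an analysis with close to 5% error and, at worst, one of 38% to 55%. This should be settled before any outcome data are analysed.

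**What to change.** Replace the corresponding text in 11.1 and 11.6 with the following.

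1. **SQI.** Define one mean post-surgical SQI per subject over the two weeks, and compare arms by linear regression on arm and the subject's mean pre-surgical SQI. Report the adjusted difference with a 95% confidence interval.
2. **QoL.** Replace the ANOVA with a linear mixed model containing arm, time, arm-by-time, baseline QoL and a term for within-subject correlation, using all available post-surgical visits. Name one primary contrast in advance, either a single visit or the average over visits, and treat the others as secondary.
3. **Rank-based alternative.** If one is kept for the arm comparison, use Mann-Whitney on the per-subject change or summary. Remove the signed-rank test from that role, and remove Mann-Whitney from the role for three or more variables.

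Other covariance choices would also be acceptable. The essential parts are the SQI summary, a method that recognises the subject, and the primary contrast. The change needs no new data, visits or subjects; it costs SAP wording and a little more analysis work with the biostatistician the plan already foresees.
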